**Table of contents****LIST OF ABBREVIATIONS AND RELEVANT DEFINITIONS**

AE	Adverse Event
CTCAE	Common Terminology Criteria for Adverse Events
CRT	ChemoRadiotherapy
NeoCRT	Neoadjuvant chemoradiotherapy
DVH	Dose Volume Histogram
EC	Esophageal cancer
GCP	Good Clinical Practice
hs-CRP	High sensitivity C-reactive protein
hs-TNT	High sensitivity troponin T
METC	Medical research ethics committee (MREC); in Dutch: Medisch ethisch toetsing commissie (METC)
NSCLC	Non small cell lung cancer
NTCP-model	Normal Tissue Complication Probability model
NT pro BNP	N-terminal pro-B-type natriuretic peptide
PDRP	Prospective Data Registration Program
OS	Overall survival
RT	Radiotherapy
(S)AE	(Serious) Adverse Event
Sponsor	The sponsor is the party that commissions the organisation or performance of the research, for example a pharmaceutical company, academic hospital, scientific organisation or investigator. A party that provides funding for a study but does not commission it is not regarded as the sponsor, but referred to as a subsidising party
SUSAR	Suspected Unexpected Serious Adverse Reaction
WMO	Medical Research Involving Human Subjects Act (in Dutch: Wet Medisch-wetenschappelijk Onderzoek met Mensen

## SUMMARY

**Rationale:** Radiation-induced cardiac and pulmonary toxicity after treatment for intra-thoracic tumors is a clinically relevant problem, which may jeopardize the benefit of (neo-adjuvant) (chemo) radiotherapy. Although cure rates are rising since the introduction of neo-adjuvant chemoradiation (neo-CRT) as current standard treatment for esophageal cancer (EC), recent studies showed that there is a substantial risk of non-cancer treatment-related death in these patients [1–6]. Furthermore, this risk is underestimated as the cause of death of many patients remains unknown, since the distinction between tumor related and non-cancer related death can be difficult.

Cardiac and pulmonary toxicity and its interaction as seen in pre-clinical studies might explain for these unknown deaths as suggested in several clinical studies [6–9]. Clinical imaging studies performed shortly after treatment showed changes in different cardiac function parameters, all related to radiation dose parameters [10–13]. Systematic imaging studies analysing subclinical toxicities at longer follow up have never been performed, most probably because of poor survival rates. However, identification of the magnitude of (subclinical) cardiopulmonary toxicity, by performing several cardiopulmonary function tests, is essential in this patient group as this toxicity is most likely the cause of the increased mortality after thoracic radiotherapy. For future perspectives, these results can be used to select the best diagnostic methods for a prospective cohort study to develop prediction tools for cardiopulmonary toxicity. Finally, this might lead to optimization of radiotherapy dose-distributions (including patient selection for proton therapy) and hopefully reduce radiation induced cardiopulmonary toxicity and improve overall survival.

### **Objective:**

The main objective of this study is to determine the most suitable diagnostic test to identify cardiopulmonary (dys)function in EC survivors treated with neo-CRT followed by surgical resection. Furthermore, we want to estimate the difference in cardiopulmonary (dys)function in EC survivors treated with neo-CRT followed by surgical resection compared to EC survivors who were treated with surgical resection alone.

**Study design:** Cross-sectional pilot study

**Study population:** 40 EC patients who were treated with curative intent by esophageal resection with or without neo-CRT

**Intervention (if applicable):** Not applicable.

**Main study parameters/endpoints:**

As this is an exploratory pilot study to determine the most suitable diagnostic tests for future studies, there will be several endpoints related to (sub)clinical cardiopulmonary dysfunction. Signs of myocardial ischemia, systolic or diastolic dysfunction, rhythm and valve disorders, pericardial effusion and fibrosis, myocardial fibrosis, focal wall motion disorders and coronary calcifications will be analyzed. The cardiopulmonary (dys)function in EC survivors treated with neo-CRT followed by surgical resection will be compared to cardiopulmonary (dys)function in EC survivors treated with surgical resection alone.

**Nature and extent of the burden and risks associated with participation, benefit and group relatedness:** Several tests will be performed at one time point, 5-10 years after given treatment. If the findings of the test indicate cardiovascular complications, the patient will be referred to the cardiologist for further analysis and/or preventive measures. As one of the tests, cardiac MRI, including gadolinium (Dotarem 0.2 mmol/kg) enhancement will be performed. Potential side effects of gadolinium include brief headache, nausea (feeling sick) and dizziness for a brief time following the injection. Allergic reactions are rare. Furthermore, a cardiac CT scan will be performed with a total radiation exposure of 0.6 mSv (less than a third of the annual background radiation dose), the risks will be minimal.

## 1. INTRODUCTION AND RATIONALE

### *Background*

Increasing numbers of patients with intra-thoracic tumours are currently treated with curatively intended combined modality strategies such as chemoradiation (CRT) either in the neo-adjuvant setting followed by surgery or as definitive treatment. Due to improved outcome resulting from the addition of chemotherapy to radiotherapy (RT) and due to the clinical introduction of neo-CRT prior to surgery, the prevalence of EC survivors is rising [5,14,15]. Therefore, the absolute number of patients at risk for treatment-related toxicity is rising as well.

There is increasing evidence that radiotherapy induces cardiac and pulmonary damage. In esophageal cancer patients, pericarditis during and shortly after radiotherapy is the most frequently observed side effect, which should be regarded as an acute inflammatory effect [16] . In the first year after treatment, wall motion disorders with changes in end diastolic volume have been observed [13,17]. These wall motion disorders are most probably caused by changes in the microvasculature. In addition, increased rates of coronary artery disease, myocardial infarctions, heart failure, as well as pericarditis, arrhythmia and valvular disorders have been observed, and may appear after longer latency times [18–20]. Systematic imaging studies analysing subclinical toxicities at longer follow up have never been performed, most probably because of poor survival rates. Preclinical studies indicate cardiopulmonary changes not only relate to the radiation dose given to the heart but also to the dose given to the lung [8,21]. The mechanism behind this phenomenon seems to be an increased pressure in the pulmonary arteries due to vascular fibrosis which leads to diastolic dysfunctioning of the heart due to a volume overload.

Furthermore, the results of several clinical studies suggested that some severe treatment-related morbidity and mortality remains unrecognized but is associated with radiation exposure to the heart and lungs. For example, the meta-analysis on the added value of postoperative radiotherapy after surgical resection for non-small cell lung cancer (NSCLC) revealed significantly worse overall survival (OS) in patients receiving post-operative radiotherapy [2], suggesting that thoracic radiation causes lethal toxicities of the lungs and/or mediastinal structures. In a dose escalation trial in NSCLC a significantly worse OS was seen in the high dose group. Overall survival turned out to be associated with the radiation dose to the heart [1]. In EC the introduction of newer techniques, like IMRT, significantly reduced the risk on cardiac death [9,22]. Furthermore, in a randomised trial comparing neo-adjuvant chemotherapy to neo-

CRT, neo-CRT had a significantly better response rate, however this did not result in a survival benefit. An explanation was found in a higher rate of non-cancer related death already during the first year of follow up [3].

In summary these data demonstrate that thoracic radiotherapy induces not only clinical but also subclinical toxicity, which might explain the unrecognized grade 5 toxicity, as a result of high dose thoracic radiotherapy. Identification of the magnitude of (subclinical) cardiopulmonary toxicity, by performing several cardiopulmonary function tests, is essential in this patient group as this toxicity is most likely the cause of the increased mortality after thoracic radiotherapy. For future perspectives, these results can be used to select the best diagnostic methods for a prospective cohort study to develop prediction tools for cardiopulmonary toxicity.

#### *Patient population*

As many of our EC patients are older and have cardiopulmonary problems as a result of their age, co-morbidities or lifestyle habits, we would like to compare a cohort of patients treated for EC who did or did not undergo (chemo)radiotherapy.

A cohort of these patients is available, as neo-CRT has become standard treatment since 2012 after the publication of the so-called CROSS trial, demonstrating an important survival benefit in the group that received neo-CRT followed by surgery compared to patients treated with surgery alone. During this time period and the time period shortly before and after, patients were treated either with or without neo-CRT. In this time period we did not select patients on cardiopulmonary co-morbidities or age, so we expect comparable groups. Part of these patients were already retrospectively analyzed and compared on short term (within 90 days) morbidity and mortality after resection [23]. These data were published in 2013. We demonstrated an increased incidence of pneumonia and rhythm disorders in patients treated with neo-CRT, but no difference was noted in neither hospital and intensive care unit stay nor in mortality or overall morbidity between these two groups. As these patients were treated in the time period 2000-2012 and thus will have a 5-15 years follow up there is a sufficiently large patient cohort available to prospectively analyze clinical and subclinical cardiac changes and/or toxicities.

*Which tests would be interesting at longer follow up or study parameters*

As mentioned in the introduction, the main focus of this study is (subclinical) cardiopulmonary (dys)functioning. The most important late (subclinical) toxicities we expect to find at longer follow up are: diastolic dysfunction, coronary artery disease, cardiac wall motion disorders, heart failure, pulmonary hypertension, pericardial effusion and/or constriction, cardiac arrhythmia and valve disorders. A number of these endpoints will eventually result in heart failure.

- Anamnesis and physical examinations will be performed in these patients
- In case a pulmonologist or cardiologist has been consulted, additional information will be collected from hospital records of these specialists.
- Radiotherapy treatment parameters will be collected from our database in case the patient was treated with radiotherapy.
- 6 minute walking test
- Echocardiogram
- CT scan
- Cardiac MRI scan
- ECG

Laboratory tests: NT-pro BNP, cholesterol, CRP and hs-TNT, eGFR, HbA1c, hematocrit.

## **2. OBJECTIVES**

Primary Objectives:

The main objective of this study is to determine the most suitable diagnostic test to identify cardiopulmonary (dys)function in EC survivors treated with neo-CRT followed by surgical resection. Furthermore, we want to estimate the difference in cardiopulmonary (dys)function in EC survivors treated with neo-CRT followed by surgical resection compared to EC survivors who were treated with surgical resection alone.

1. To determine the differences in clinical cardiac and pulmonary events, (cardiac ischaemia, heart failure, arrhythmia, valve disorders, pulmonary hypertension, COPD) as clinically diagnosed since treatment between patients treated with neo-CRT and surgery alone.
2. To determine the difference in other (subclinical) parameters as tested by echo cardiogram, 6 minute walking test, CT scan, MRI scan and biomarkers.
3. To analyse the current CAC scores in both patient groups.
4. To determine the difference between the baseline and current CAC scores.

5. To determine the difference between ECG findings currently and on baseline.
6. To correlate the different subclinical imaging parameters to the radiation dose given to the heart and lungs
7. To correlate CAC scores with the given dose distribution on plannings CT scan

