### **3. ENDPOINTS**

As this is an exploratory pilot study to determine the most suitable diagnostic tests for future studies, there will be several endpoints related to (sub)clinical cardiopulmonary dysfunction. Signs of myocardial ischemia, systolic or diastolic dysfunction, rhythm and valve disorders, pericardial effusion and fibrosis, myocardial fibrosis, focal wall motion disorders and coronary calcifications will be analyzed.

The cardiopulmonary (dys)function in EC survivors treated with neo-CRT followed by surgical resection will be compared to cardiopulmonary (dys)function in EC survivors treated with surgical resection alone.

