## **10. STATISTICAL ANALYSIS**

### **10.1. Primary study parameter(s)**

Different cardiopulmonary parameters will be presented by means and standard deviations and will be compared between the groups using an independent t-test, with Bonferroni correction if applicable.

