### **10.2. Other study parameters**

Risk factors for cardiac and pulmonary complaints will be presented in frequency tables and tested for statistical significant differences between both groups using an independent t-test

Location of focal wall abnormalities and arteriosclerosis and its relation to high dose regions will be presented in a table.

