### **11.4. Benefits and risks assessment, group relatedness**

The risk of participation in this study is very low. Patients have to visit the hospital once. The patient will have to stay in the hospital for approximately 6-8 hours. Within this time period anamnesis, questionnaires, physical examination and additional tests will be performed.

Blood withdrawal may result in local tenderness or hematoma, which are self-limiting.

Cardiac MRI scan requires IV contrast infusion with gadolinium, with the use of gadolinium there is a very low risk of anaphylactic reactions, nausea and headache, besides, the small bore used in MRI scanning may trigger claustrophobic feelings

Echo, ECG and the walking test do not cause any harm to the patients.

CT scan will give radiation exposure but as the total dose of this cardiac CT scan is relatively low total radiation dose of 0.6 mSv (less than a third of the annual background radiation dose), the risks will be minimal.

Patients participating will be evaluated for subclinical cardiopulmonary (dys)functioning. Patients will be referred to a cardiologist or pulmonologist for early intervention if considered necessary, this might improve quality of life or even life expectancy.

The results of this pilot study will form the basis for a subsequent prospective observational cohort study in which the most promising tests and clinical endpoints will be used to assess correlations with radiotherapy dose metrics with the ultimate aim to develop prediction models. These models can be used for model-based radiotherapy treatment plan optimization and to select patients for the best radiation technique, e.g. proton therapy.

Furthermore, the result of such a prospective cohort study might indicate the necessity of preventive measures for cardiopulmonary toxicity in the future.

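### The main objective is to choose the most suitable diagnostic test, but the only analysis stated for the primary parameters is a between-group t-test on each one, which does not compare the tests with each other

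*Protocol*

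**What the plan says.** Section 2 (and the Summary) opens with the choice of test; the main objective is to "determine the most suitable diagnostic test to identify cardiopulmonary (dys)function in EC survivors treated with neo-CRT followed by surgical resection". The group comparison follows as an addition: "Furthermore, we want to estimate the difference in cardiopulmonary (dys)function in EC survivors treated with neo-CRT followed by surgical resection compared to EC survivors". Section 3 gives the same purpose, with tests in the plural: "As this is an exploratory pilot study to determine the most suitable diagnostic tests for future studies, there will be several endpoints". Section 11.4 says what the result is for: a later cohort in which "the most promising tests and clinical endpoints will be used to assess correlations with radiotherapy dose metrics".

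Section 10.1, on the primary parameters, plans means and standard deviations, with each parameter "compared between the groups using an independent t-test, with Bonferroni correction if applicable". Section 10.2 adds two items. Risk factors are tabulated and "tested for statistical significant differences between both groups using an independent t-test". For lesions, "Location of focal wall abnormalities and arteriosclerosis and its relation to high dose regions will be presented in a table". Objectives 6 and 7 in section 2, and the cardiac CT and radiotherapy plan parts of section 8.2, also foresee relating imaging parameters and CAC scores to dose.

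Section 7 sets 40 patients, 20 per group, without a calculation. Section 8.2 schedules every participant for the walking test, ECG, laboratory tests, echocardiogram, cardiac CT and cardiac MRI.

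**The concern.** Choosing among tests and estimating a group difference are different questions. A t-test on one parameter asks whether its mean differs between neo-CRT and surgery-alone survivors. Repeating it for every parameter gives a list of group differences. It does not say whether one test separates the groups better than another, or how sure one can be of that. One parameter reaching significance while another does not is not evidence that the first is the better test.

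The protocol does not define what makes a test most suitable or most promising. It names no performance measure or reference standard, and gives no rule leading from the group comparisons to a choice. Every participant is scheduled for every test, so the tests could be compared within patients, but the stated analysis does not use this.

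At stake is the selection of tests for the follow-on cohort, which is what the pilot is for. If the optional correction became the selection rule by default, the likely result at this size would be an empty list. Without correction it would be a handful of nominally significant parameters and no stated way to choose among them.

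**Working it through.** **1. Objective against analysis**

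| Aim (section 2) | What it needs | What is stated |
|---|---|---|
| Most suitable test | A performance measure per test, and a comparison between tests | None in 10.1 or 10.2 |
| Difference between neo-CRT and surgery alone | A between-group comparison per parameter | t-test per parameter (10.1) |

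Section 10.2 compares risk factors between groups and tabulates lesion location against dose. Neither compares diagnostic tests.

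**2. If Bonferroni were the selection rule**

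The protocol gives no alpha, effect size or number of parameters, so it has no figure to reproduce. From the documents: n = 20 per group, and 17 numbered echocardiographic items in section 8.2. Assumed: two-sided alpha 0.05, complete data, true difference d in SD units, and m parameters in the family. I use m = 30 as a round figure for the echo items plus MRI, CT, laboratory and walking-test values.

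Power comes from the noncentral t with df = 2 × 20 − 2 = 38, noncentrality d × √(n/2) = d × √10, and level 0.05/m. At d = 0.8 the noncentrality is 0.8 × 3.162 = 2.53.

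| m | Level | Power, d = 0.5 | Power, d = 0.8 | Power, d = 1.0 | d detectable with 80% power |
|---|---|---|---|---|---|
| 1 | 0.05 | 34% | 69% | 87% | 0.91 |
| 17 | 0.00294 | 7% | 28% | 50% | 1.28 |
| 30 | 0.00167 | 5% | 22% | 43% | 1.35 |

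Suppose one parameter truly differs by 0.8 SD and the rest do not differ. The chance that nothing is flagged is then at least 1 − power − (m − 1) × 0.05/m:

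- m = 17: 1 − 0.278 − 16 × 0.00294 = 0.675
- m = 30: 1 − 0.219 − 29 × 0.00167 = 0.733

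In a simulation with m = 30, one effect of 0.8 SD, five of 0.4 SD and the rest zero, nothing was flagged in about 66% to 73% of studies as the correlation between parameters went from 0 to 0.5. Uncorrected, about 3 of the 30 had p < 0.05. The result depends on the largest effect: at 1.2 SD instead of 0.8 (correlation 0.3), nothing was flagged in about 31%.

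**3. How uncertain a choice is**

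Simulation of 20,000 studies, 20 per group, one test with a true difference of 0.8 SD and the others 0.5 SD. The largest |t| picked the best test in 74% to 81% of studies with 2 tests, and in 42% to 53% with 6 tests (correlation 0 to 0.5). Separate p-values do not show this uncertainty.

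On the AUC scale at d = 0.8:

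- A = Φ(0.8/√2) = 0.714
- Hanley-McNeil terms: Q1 = A/(2 − A) = 0.555 and Q2 = 2A²/(1 + A) = 0.595
- SE = √{[A(1 − A) + 19(Q1 − A²) + 19(Q2 − A²)]/400} = 0.082
- 95% interval: ± 1.96 × 0.082 = ± 0.16, that is 0.55 to 0.87

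**4. Does rescaling change the order?**

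With equal groups and complete data, |t| = |d| × √10 for every parameter, where d is now the observed standardised difference. Ordering by |t|, by p-value or by |d| is the same. What an estimate with its interval adds is size and uncertainty, not a different order.

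**The case against.** The strongest reply is that this is an exploratory pilot, that the tests can be ranked from the planned output, and that the rest is detail for a SAP, which is not at hand. Much of this stands.

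- A reader might infer that t-tests on different units cannot be ranked. They can. The t statistic is unit-free, step 4 shows that it orders parameters as the standardised difference does, and 10.1 already plans the means and SDs from which that difference follows. So ranking by standardised difference cannot be credited with finding the best test more often than ranking the protocol's own t-tests.
- A reader might infer that the protocol selects tests by corrected significance. It does not say so. Bonferroni is optional and its family is not fixed, so step 2 shows only what would follow from that use.
- A reader might infer that nothing planned bears on the choice. The planned dose correlations and the lesion table do bear on which tests look promising for a cohort concerned with dose.
- A shortlist is a legitimate result for a pilot, and section 3 speaks of tests in the plural. Bootstrap details may well belong in a SAP.

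What the reply does not remove is the mismatch. This is not only detail left for later: the protocol fixes an analysis for its primary parameters, and that analysis answers the second aim. The pilot label excuses the missing power calculation. It does not excuse a main objective with no stated comparison behind it.

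**Conclusion.** The point holds in this form: the only analysis stated for the primary parameters addresses the group difference. It neither compares the diagnostic tests nor shows how uncertain a choice between them is, although that choice is the main objective. This follows from the text and needs no assumption.

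The figures are illustrations. At an assumed 0.8 SD with 20 per group, power falls from 69% for one parameter to 28% with Bonferroni over 17 and 22% over 30. Used as a selection rule, the correction would then often leave nothing to carry forward. Larger true effects weaken that statement; a smaller family would too.

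The documents do not support saying that t-tests cannot order the parameters, or that the choice of tests would rest on no planned analysis at all. The change should be made, because the result feeds directly into the next study and the remedy is cheap.

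**What to change.** Add to section 10.1 an analysis for the main objective:

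- Report each parameter's standardised neo-CRT versus surgery difference, or its AUC for separating the groups, with a 95% CI.
- Compare tests by a bootstrap that resamples patients within each group, so that the within-patient pairing of tests is kept.
- Carry forward a shortlist on estimate, interval and completion rate, not on a Bonferroni-corrected p-value.
- State that this measures sensitivity to treatment group, not diagnostic accuracy, because the protocol names no reference standard for dysfunction.

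Alternatively, keep 10.1 and reword the main objective as exploratory estimation of group differences.

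The cost is a few lines of text and some extra analysis of data already being collected. The downside is imprecision: with an AUC interval of about ±0.16 at 0.8 SD, the pilot can support a shortlist but hardly a single winner, and the protocol should say so.
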